#### **Statistical analyses**

Preliminary analyses: Prior to the formal analyses, we will conduct exploratory data analysis by examining the distributions of the key variables using descriptive statistics and graphic tools. In particular, baseline variables (demographics, concussion history and injury severity characteristics) will be examined to determine whether outliers are present. The baseline characteristics of the 100 enrolled boxers/MMA fighters will be compared with 80 controls using linear regression and two sample testing. Continuous variables (primary and secondary outcomes) will be summarized through standard measures of central tendency and spread including means, medians, standard deviations and IQRs. Frequency distributions will be calculated for categorical variables (CBF/CVR, post-concussion symptoms,

neuropsychological measurements). Data transformations will be used if needed to produce variables that conform to the distributional assumptions underlying the analytic techniques. Both primary and secondary outcomes will be evaluated under the intent-to-treat principle, meaning that all available data on all randomized participants, regardless of adherence to the study protocol, will be included and analyzed according to the treatment assignment, although compliance will be closely monitored via pill counting. Statistical analysis will be performed with SAS (SAS Institute, Cary, NC, USA) and R software.

Primary analyses: Our primary analysis (**Aim 1**) will be driven by the primary hypothesis that administration of single or multiple doses of sildenafil will improve CBF/CVR, lower symptoms and improve cognition. Boxplots of CBF and CVR of concussed boxers after sildenafil and placebo periods will first be plotted and compared with values at Day 1-3 and 30 post-TBI as well as with the 80 controls.

Also, we will assess the treatment effect of sildenafil on post-concussive symptoms and cognitive performance using two-sample t-test similarly as in the primary aim, but with the secondary endpoints of symptoms. On day 1 and 30 after injury we will then calculate the difference in CBF/CVR and each of the post-concussive symptom assessments and cognitive assessments after the single treatment of sildenafil. Also, we will assess the post-concussion correlations of CBF/CVR and cognitive performance by calculating the cross-sectional Pearson correlations of CBF/CVR with symptom inventory and neuropsychological CDEs collected at Day 1 and 30 after TBI. Correlations will be calculated separately and jointly at each time point, and for each of the subdomains of neuropsychological CDEs. Multiple comparisons will be adjusted by controlling the false discovery rate (FDR).

Our secondary analyses will consist of assessing the treatment effect of sildenafil therapy on brain biomarker levels using two-sample t testing, but with the secondary endpoints of symptoms. We will then calculate the difference in brain biomarker levels at the beginning of the sildenafil therapy and after the treatment period (Day 30 vs Day 1-3). Scatter plots including both arms will be generated based on the calculated differences and two linear regression models with changes in brain biomarkers as outcomes, and changes in symptoms as independent variables will be fit to assess the association between the recovery of the TBI-related markers. Potential confounders such as gender and treatment arm indicator will be adjusted in the model.

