The participants in **group 1** (single therapy) will consist of the active boxers/MMA fighters that experience significant sub-concussive blows or a concussion during competition. In this group, 65, professional male/female boxers/MMA fighters within the North Texas region will be screened and about 50 concussed athletes will be enrolled. The athletes that have at least 25 blows to the head and a Symptom Score > 1 on at least 3 items from the Rivermead Post-Concussion Questionnaire following their fight will be enrolled in this study. The research subjects will be treated with sildenafil (60mg), once at 2 hours after experiencing a concussion.

**Group 2** will consist of the active boxers/MMA fighters that experience significant subconcussive blows or a concussion during competition. In this group, 65, professional male/female boxers/MMA fighters within the North Texas region will be screened and about 50 concussed athletes will be enrolled. The athletes that have at least 25 blows to the head and a Symptom Score > 1 on at least 3 items from the Rivermead Post-Concussion Questionnaire following their fight will be enrolled in this study. Once enrolled, the subjects will be treated with sildenafil (60mg) once-a-day for 14 days.

**Healthy Control group:** In this study, 80, age (between 18 and 35)-matched healthy controls will be enrolled. The control subjects will participate in neuropsychological testing, blood/saliva collection, and the MR imaging procedures. Healthy controls will be tested in group 1 (n=40) and 2 (n=40) and randomized to receive either sildenafil or placebo in this group.

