## 4.2 STUDY ENDPOINTS

## 4.2.1 PRIMARY ENDPOINT:

To determine if sildenafil administration improves CBF/CVR, reduces symptoms, and improves cognitive performance in concussed boxers/MMA fighters. Hypothesis: Both single and multiple sildenafil therapy improves CBF/CVR, symptoms, and cognition in concussed boxers. Also, long-term administration of daily doses of sildenafil to concussed boxers/MMA fighters is well tolerated. Following injury, we will enroll 100, active boxers/MMA fighters and 80, controls into a double-blind, placebo-controlled study. At a 1:1 ratio, the subjects will receive a single treatment of either placebo or sildenafil. The purpose of this study is to determine if sildenafil treatment improves CBF/CVR, reduces symptoms, and improves cognitive outcomes. In this study we will treat the injured athletes once (within 2 hours of injury) or daily (for 14 days) to determine if sildenafil improves outcomes. Previous clinical studies conducted by our research group, we found that sildenafil treatment (60mg) is tolerable within the TBI population. The athletes will maintain a daily diary of symptoms. At day 1-3 and 30 after injury, the CBF/CVR MR imaging procedures, the Rivermead Post Concussion Symptom Questionnaire, and neuropsychological assessments (NIH Common Data Elements) will be conducted to study the effect of sildenafil therapy. Blood (8cc) and saliva will also be collected to measure brain biomarkers of injury. Tolerability (blood testing and symptom reporting) assessments will be conducted throughout the study to ensure that the symptomatic boxers tolerate multiple, daily doses of sildenafil.

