# 6.1.5 DOSING AND ADMINISTRATION

STU032018-063, [name], FormA-ResearchProtocol, Mod\_6, 11-25-19 (1) NIH-FDA Clinical Trial Protocol

In the first and second group, the participants will be administered either a single-dose or 14 pills of placebo or sildenafil (60mg) after suffering a concussion. The first dose will be taken at 2hours after injury.

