#### Power analysis and sample size justification

We conducted a power analysis based on the primary endpoints of change in CVR and CBF and correlation of CBF/CVR and symptoms/cognition. Based on the preliminary results, we assume the average changes in CVR between treatment and placebo has an effect size of 0.86. With 50 concussed boxers in each arm, assuming that the correlation between the outcome measures at Day 1-3 and 30 is 0.2, we will achieve 80% power to detect difference in CVR changes comparing sildenafil and placebo effects. If the correlation is 0.5 among outcome measures at all time-points, then with 80% power we only need 34 concussed boxers in each arm. Table 1 demonstrates the needed sample size under a range of effect sizes and within-subject correlations. To understand the correlation between the CVR and post-concussive symptoms among the 50 enrolled boxers (for each group) assessed at three time points, we will have 82.9% power to detect a correlation of 0.4 based on the preliminary results in Table 1 with 95% confidence level.

	Correlation between 3, time-points (rho)							
	0	0.2	0.3	0.5	0.6	0.7	0.8	
Corresponding SD	1.414	1.265	1.183	1	0.894	0.775	0.632	
Effect size	Sample size needed							
0.7	46	38	33	25	21	16	12	
0.86	32	26	23	18	15	12	9	
1	24	20	18	14	12	10	8	
1.2	18	15	14	11	9	8	6	

Table 1: Sample size for each treatment and placebo group under a range of effect sizes and within-subject correlations to achieve 80% power.

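### The hypothesis covers the single dose and the 14-day course, but the analysis has no regimen-specific test or pooling rule, and 50 per arm is a pooled count: each regimen has about 25 per arm

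*Combined protocol and SAP*

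**What the plan says.** - **Hypothesis.** Section 4.2.1: "Both single and multiple sildenafil therapy improves CBF/CVR, symptoms, and cognition in concussed boxers". The primary analysis in Section 10.1 (Statistical analyses) is driven by the hypothesis that "administration of single or multiple doses of sildenafil will improve CBF/CVR, lower symptoms and improve cognition".
- **Groups.** Section 4.1 forms Group 1 (one dose) and Group 2 (daily for 14 days). For each it says that "about 50 concussed athletes will be enrolled". Section 6.1.5 gives placebo or sildenafil in both groups, and Sections 4.1, 10.1 and 10.2.1 set 1:1 allocation.
- **Analysis.** Section 10.1 assesses symptoms and cognition "using two-sample t-test similarly as in the primary aim", with no regimen named. The next sentence calculates the difference in cerebral blood flow (CBF)/CVR and in each symptom and cognitive measure "after the single treatment of sildenafil". The fallback under Alternative strategies is a rank-sum test, also without reference to regimen.
- **Power.** "With 50 concussed boxers in each arm", an effect size of 0.86 and a correlation of 0.2, the plan claims 80% power for the CVR comparison. At a correlation of 0.5 it says 34 per arm suffice.
- **Dropout.** Section 10.2.1 expects 10-20% and plans to enrol 110-120. Section 4.1, and the drug treatment paragraph of Section 10.2.1 itself, say 100 are enrolled.

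**The concern.** A hypothesis that two regimens each work needs an estimate and a test for each, or a stated reason to combine them. Section 10.1 provides neither. The analyst would have to leave out the 14-day course, pool one dose with fourteen, or choose after seeing the data. By Day 30 the two regimens differ by 1 dose against 14, so a pooled Day 30 contrast averages two quite different exposures and cannot show which of them had an effect.

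The power statement hides the gap. Fifty per arm is reached only by pooling, so it says nothing about the power of either regimen-specific claim. The Stopping rules text says these data will be used to power a definitive study, and that study would need regimen-specific estimates.

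**Working it through.** **Inputs** (Section 10.1, Power analysis, unless noted)
- Effect size for CVR change: 0.86.
- SD of change: √(2(1 − ρ)), which matches the plan's table: √1.6 = 1.265 at ρ = 0.2 and √1.0 = 1 at ρ = 0.5.
- Athletes: 100 in two regimen groups of about 50, allocated 1:1 (Sections 4.1 and 10.1).
- Alpha: not stated for CVR. A 95% level is given only for the correlation. **Assumed:** two-sided 0.05, with 0.025 shown for a split over two regimens.
- Test: two-sample t, noncentral-t power with noncentrality (0.86/SD) × √(n/2) and 2n − 2 degrees of freedom.

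**Count per arm within a regimen:** 100 / 2 regimens / 2 arms = 25.

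**Standardised difference:** 0.86/1.265 = 0.68 at ρ = 0.2; 0.86/1 = 0.86 at ρ = 0.5.

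**The plan's own figure first.** At 50 per arm and ρ = 0.2, noncentrality is 0.68 × √25 = 3.40 and power is 92%, not the stated 80%. At 34 per arm and ρ = 0.5, power is 94%, not 80%. So the stated figures do not reproduce at two-sided 5%. An undocumented two-sided alpha of 0.0125 comes close (50 and 32 per arm). This is a separate error in the power text and should not be read as part of the loss from splitting by regimen.

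**Power per regimen**

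| n per arm | alpha | ρ = 0.2 | ρ = 0.5 |
|---|---|---|---|
| 50 (pooled) | 0.05 | 92% | 99% |
| 25 | 0.05 | 65% | 85% |
| 25 | 0.025 | 54% | 76% |
| 24 | 0.05 | 64% | 83% |
| 20 | 0.05 | 55% | 76% |

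**Dropout.** With 110-120 enrolled: 110 × 0.9 = 99 and 120 × 0.8 = 96 remain, so 99/4 ≈ 25 or 96/4 = 24 per arm per regimen. If only 100 are enrolled and 20% drop out: 80/4 = 20.

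**Size needed for 80% power in each regimen:** 35 per arm (ρ = 0.2) or 23 (ρ = 0.5) at 0.05; 43 or 28 at 0.025.

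**If the regimens are pooled and only one works.** With equal groups the average effect is (0.86 + 0)/2 = 0.43. At 50 per arm this gives about 39% power (ρ = 0.2) or 57% (ρ = 0.5), ignoring the extra spread that the mixture adds.

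**The case against.** **The SAP does not restrict itself to the single dose.** A reader might infer from the single-treatment phrase that the 14-day course is never tested. The documents do not support that. Section 10.1 frames the primary analysis as single or multiple doses, its intent-to-treat rule covers all randomised participants, and its t-tests name no regimen. The phrase sits in a sentence about calculating a difference. Section 4.2.1 uses similarly loose wording for all athletes before describing both regimens. It is more likely loose drafting than a restriction. This stands; what remains is that the 14-day course has no specified test and no pooling rule.

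**Fifty per arm is correct for a pooled comparison.** This also stands. The fault is the mismatch with a hypothesis about each regimen. Pooling is also less objectionable at Day 1-3, when the daily group has had only 1-3 days of drug (Section 9, Trial Safety).

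**The power loss is not uniform.** At ρ = 0.5 and unadjusted 5%, 25 per arm gives 85%. One cannot say that neither regimen can reach 80%.

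**Requiring both regimens to succeed is only one reading.** Multiplying the powers gives 0.654² = 43% and 0.846² = 72% if success means both. Section 4.2.1 says both, but Section 10.1 says single or multiple. Under the latter, at least one success has probability 1 − (1 − 0.654)² = 88% and 1 − (1 − 0.846)² = 98%. These treat the regimens as independent, with unadjusted alpha. Neither pair should carry the argument until the plan defines success.

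**Table 1 lists 26 per group at 0.86 and ρ = 0.2.** This does not defend 25 per arm. All 28 cells reproduce as a one-sample or paired t-test at two-sided 0.0167 and 80% power, not as a two-arm comparison. A two-sample t-test with 26 per arm gives 67% at 5%.

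**It is a pilot.** The study schematic is titled as one. That lowers the demand on power, but does not remove the need to say how two regimens are analysed.

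**Conclusion.** The concern holds in this form: the plan hypothesises an effect of each regimen, but specifies no regimen-specific test, regimen term or pooling rule, and states CVR power only for the pooled count. Per regimen, about 25 per arm gives 65% power at ρ = 0.2 and 85% at ρ = 0.5, or 54% and 76% with alpha split. After dropout the figures at 5% are 64% and 83% (24 per arm, if 120 are enrolled and 20% leave) or 55% and 76% (20 per arm, if 100 are enrolled and 20% leave). The enrolment statements conflict, so neither dropout case can be taken as the plan's.

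All of this rests on an assumed two-sided 5% level, a two-sample t-test, the plan's effect of 0.86 for both regimens, and its formula for the SD of change. The absence of a regimen-specific analysis does not depend on any of these. It should be settled before unblinding, because a later choice to pool or separate would be driven by the data.

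**What to change.** 1. Analyse by the groups already formed: sildenafil minus placebo within Group 1 and within Group 2, plus an overall effect stratified by regimen.
2. Name in advance which contrast is primary and how alpha is shared among the contrasts.
3. Replace the single-treatment phrase in Section 10.1 with wording that covers both regimens.
4. Label 50 per arm as pooled only. State alpha, and give power for about 25 per arm in each regimen.
5. Treat the treatment-by-regimen interaction as exploratory. No section clearly says that athletes are randomised between regimens, so it may compare groups that were not formed by randomisation.
6. Reconcile enrolment of 100 (Sections 4.1 and 10.2.1) with 110-120 (Section 10.2.1), and correct the 80% figure for 50 per arm as a separate item.

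Cost: SAP wording and a less favourable power statement, with no extra participants.

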## 10 STATISTICAL CONSIDERATIONS

#### 10.1 STATISTICAL AND ANALYTICAL PLANS

#### STATISTICAL ANALYSIS PLAN

#### Study design and randomization scheme

Once eligibility is confirmed, based upon defined inclusion and exclusion criteria, randomization will occur within 2 hours of a bout. The placebo-controlled double-blind design will diminish concern about predictability of treatment assignments. The unblinded study biostatistician will prepare a randomization schedule. Randomization will be 1:1 sildenafil:placebo, and will be in blocks of 2. Treatment allocation will be determined via a computer program that automatically generates random digits. Investigators associated with this study will not have access to the randomization schedule. The randomization program will also record the assignments to the corresponding boxers in the database and will display the assignments on the screen for action by the study coordinators.

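### The planned CBF/CVR correlations with symptoms and cognition carry no treatment-arm term; wherever arms are pooled, a drug effect on both variables adds a modest correlation of its own

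*Combined protocol and SAP*

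**What the plan says.** The primary-analysis text of Section 10.1 describes "calculating the cross-sectional Pearson correlations of CBF/CVR with symptom inventory and neuropsychological CDEs collected at Day 1 and 30 after TBI". It adds: "Correlations will be calculated separately and jointly at each time point, and for each of the subdomains of neuropsychological CDEs", with false discovery rate control for multiplicity. It mentions no arm stratum, arm covariate or partial correlation.

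The primary hypothesis in the same section is that "administration of single or multiple doses of sildenafil will improve CBF/CVR, lower symptoms and improve cognition". Section 6.1.5 places the first dose two hours after injury, so on that timing both visits named for the correlations follow treatment. On allocation the plan states: "Randomization will be 1:1 sildenafil:placebo, and will be in blocks of 2".

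Arm does appear in the next paragraph, for the regressions of biomarker change on symptom change: "Potential confounders such as gender and treatment arm indicator will be adjusted in the model".

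The power section counts the correlation among the quantities it was based on. It describes the analysis as "among the 50 enrolled boxers (for each group) assessed at three time points" and claims "82.9% power to detect a correlation of 0.4 based on the preliminary results in Table 1 with 95% confidence level". For the drug effect on CVR it says "we assume the average changes in CVR between treatment and placebo has an effect size of 0.86".

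**The concern.** If sildenafil does what the plan hypothesises, arm is a common cause of the two variables being correlated. In a sample mixing sildenafil and placebo athletes, the treated half then tends to have higher CVR and lower symptom scores. That shift in means alone gives a negative CVR–symptom correlation, and a positive one with cognition, even if CVR says nothing about symptoms among athletes on the same treatment.

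The power section says that the aim is to understand how CVR and symptoms go together, and the Stopping rules paragraph says that the data will be used to design a definitive study. A coefficient that partly restates the treatment effect is a weaker basis for either purpose. The plan already treats arm as a confounder for the biomarker associations and gives no reason for leaving it out here.

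**Working it through.** **Step 1. The plan's own figure.** Inputs from the power section: r = 0.4, n = 50, 95% confidence (two-sided assumed). By Fisher's z, power = Φ(atanh(r)·√(n − 3) − 1.96) = Φ(0.4236 × 6.856 − 1.96) = Φ(0.944) = 82.8%. The plan states 82.9%, so this is a test of a plain correlation in 50 athletes. A one-sided test would give 89.6%, which does not fit.

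**Step 2. Who the 50 are.** Section 4.1 defines group 1 (single dose) and group 2 (14 days), about 50 athletes each. With 1:1 allocation each mixes about 25 sildenafil and 25 placebo athletes. The power section, however, also speaks of 50 per arm, and its table caption uses the word group for treatment and placebo. The documents support either reading. I use n = 50 for one dosing group and n = 100 for all athletes.

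**Step 3. Induced correlation.** Let d1 and d2 be the between-arm differences in CVR and in the symptom or cognition score, in within-arm SDs, and w the within-arm correlation. With equal arms,

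r = (w + d1·d2/4) / √[(1 + d1²/4)(1 + d2²/4)].

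- d1 = 0.86, from the power section. Its table uses SD = √(2(1 − ρ)) for a change, so 0.86 is in units of the single-visit SD. It is stated for changes in CVR; using it as a difference in level is my assumption.
- d2 is not in the documents. I take 0.2 to 0.86, with 0 for reference.

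For w = 0 and d2 = 0.5: (0.86 × 0.5/4)/√(1.1849 × 1.0625) = 0.1075/1.122 = 0.096. For d2 = 0.86: 0.1849/1.1849 = 0.156.

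**Step 4. Rejection rates.** These come from 40,000 simulated data sets per scenario, with normal data, equal arms, w = 0 and a two-sided 5% test.

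| d2 (assumed) | induced abs. r | plain test, n = 50 | plain test, n = 100 |
|---|---|---|---|
| 0 | 0.00 | 5% | 5% |
| 0.2 | 0.04 | 6% | 6% |
| 0.3 | 0.06 | 7% | 9% |
| 0.5 | 0.10 | 10% | 16% |
| 0.86 | 0.16 | 19% | 34% |

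The arm-adjusted partial correlation rejected about 5% of the time in every row.

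**Step 5. When a real link exists.** With w = 0.4 in the direction that the drug also pushes, the pooled value is (0.4 + 0.1075)/1.122 = 0.45 for d2 = 0.5, and (0.4 + 0.1849)/1.1849 = 0.49 for d2 = 0.86.

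**Step 6. Could arm mixing alone reach 0.4?** With w = 0 and equal effects, (d²/4)/(1 + d²/4) = 0.4 gives d²/4 = 0.667, so d = 1.63. Both effects would have to be about 1.63 SD, well above the plan's 0.86.

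**The case against.** The strongest reply is that the plan is silent rather than wrong. If a group of 50 means an arm, the correlation is computed within arm and treatment cannot confound it. This stands as far as it goes: a reader might infer that the plan commits itself to pooling the arms, and the documents do not support that. The sentence about calculating separately and jointly does not settle the matter either, since it names time points and subdomains. Even on the arm reading, an arm of 50 would pool single-dose and 14-day athletes.

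Timing also limits the point. The power section counts three time points; one is presumably baseline, before dosing, where no drug effect can enter. At Day 30, group 1 has had one dose a month before and group 2 has finished its course, so a CVR difference of 0.86 SD there is poorly supported; with no difference, nothing is induced. The schedule in Section 7.1.1 also places randomization and dispensing in the Day 1-3 column, whereas Sections 6.1.5 and 7.3.2 put the first dose at two hours. These passages need to be reconciled; I have used the two-hour timing.

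Adjustment also changes what is estimated. If the drug lowers symptoms through CVR, the between-arm part is genuine association, and adjustment removes it. That is fair, but a pooled coefficient cannot separate this route from a drug that acts on the two outcomes independently.

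Two defences fail. False discovery rate control deals with the number of tests, not with bias in each coefficient; it does mean that the 5% rates above are per test, not those of the full planned procedure. The intent-to-treat statement fixes who is analysed in which arm and adds no arm term to a correlation.

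**Conclusion.** The point holds as a should-fix matter of specification. The correlations are written without an arm term, under a hypothesis that makes arm a common cause of both variables, while the neighbouring biomarker model adjusts for it. Where arms are pooled, the induced |r| is about 0.04 to 0.16, and a true within-arm 0.4 would be overstated at about 0.45 to 0.49 (the latter for symptom effects of 0.5 to 0.86 SD). The upper figures need symptoms to move as much as CVR. All of them rest on an assumed symptom effect and on reading 0.86 as a difference in CVR level.

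A reader might go further and infer that arm mixing could manufacture the targeted correlation, or that the treatment comparison is compromised. Neither follows. The plan's own effect size falls well short of producing 0.4, and the two-sample comparisons between arms do not use these correlations. Nor does the Outcomes paragraph list the correlation as an endpoint, although the power section relies on it.

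**What to change.** In Section 10.1, replace the plain Pearson correlations with partial correlations, or an equivalent regression, adjusted for treatment arm, and for dosing group wherever the two dosing groups are combined. The biomarker model is a precedent for arm, but it does not name dosing group. State in the power section whether a group of 50 is an arm or a dosing group. The unadjusted coefficient can still be shown descriptively.

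The cost is one or two degrees of freedom. With n = 50 and arm adjusted, power for r = 0.4 is Φ(0.4236 × √46 − 1.96) = 81.9%, against 82.8% unadjusted. With n = 100 it is 98.6% against 98.7%. Estimating the correlation separately in each arm of one dosing group (25 athletes) would also remove the confounding, but with only about 51% power: Φ(0.4236 × √22 − 1.96).

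The SAP should say that the adjusted value is the within-arm association, assumed common to both arms.
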